9.5.1 Analyses of Primary Efficacy Endpoint(s)

The MRD-negative rate at the end of cycle 1 of blinatumomab is calculated as the number of subjects with MRD-negative status after treatment with blinatumomab divided by the total number of subjects in Primary Analysis Set for Primary Analysis. Exact binomial 95% CI will be summarized as well.

MRD-negative rate will also be analyzed in Full Analysis Set for final analysis. A sensitivity analysis will be performed using the Target Dose Analysis Set for the final analysis

9.5.2 Analyses of Secondary Efficacy Endpoint(s)

The secondary endpoints PFS, duration of MRD-negative status and OS will be summarized with Kaplan-Meier (KM) analyses on the Full Analysis Set for final analysis.

A sensitivity analysis will be performed on the Target Dose Analysis Set for final analysis.

9.5.3 Analyses of Exploratory Efficacy Endpoint(s)

The following exploratory efficacy endpoints will be analyzed using Primary Analysis Set at primary analysis and Full Analysis Sets at the time of final analysis.

- The MRD-negative rate will be summarized at each timepoint measured following blinatumomab treatment
- Incidence of alloHSCT (number of subjects with alloHSCT), including the methodology (Intensity of Conditioning Regimen and Donor Type) and clinical outcomes (Maximum grade of aGVHD) will be summarised.
- Relationship between pre-specified covariates mentioned in the [section 4.1](#) with MRD negative status and clinical outcomes (PFS, OS) will be explored. Subject incidence of MRD negative status, and KM estimates for the clinical outcomes will be summarized for different pre-specified covariates as the data permits
- Clinical outcomes (PFS, OS) will be analyzed by MRD status. A landmark analysis will be performed using day 75 (end of cycle 1) as the landmark time point. Subjects will be defined as MRD negative or positive based on their MRD status as of at day 75. Only subjects who are still being followed up for PFS or OS at day 75 will be included in the analysis. The KM summaries will be performed by MRD status for clinical outcomes (PFS, OS) from day 75.

The following MRD characteristics prior to treatment with blinatumomab will be summarized using the Pre-Treatment Analysis Set:

- MRD status at screening by the NGS test in PET-CT negative subjects post aHSCT will be summarized.
- Estimates of the rate and timing of MRD-negative to MRD-positive change during the 24-month run-in period will also be summarized. The run-in period will be divided into becoming MRD-positive at enrollment, MRD-positive within 6 months from enrollment and MRD-positive any time later during run-in.

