MRD status will be assessed at cycle 1 day 1 prior to blinatumomab infusion, on cycle 1 days 15 and 43, the end of the blinatumomab infusion (day 57), and 2 weeks after the end of the blinatumomab infusion (day 71 + 3 days) to evaluate disease status. A PET-CT will be performed only if a subject remains MRD-positive (day 57 of cycle 1 assessment) after blinatumomab or has clinical signs and symptoms of disease progression.

A safety follow-up visit will occur 30 days (+ 3 days) after the last dose of blinatumomab for assessment of disease-related events, adverse events, and serious adverse events. A long-term follow-up period to assess disease status and OS begins at completion of the safety follow-up visit and continues for 1 year from the first dose of blinatumomab. Subjects will be followed via clinic visit every 3 months (\pm 2 weeks) for MRD assessment and by institutional standard of care disease evaluation (PET-CT or CT) until relapse at which time the subject will be followed for survival via telephone contact.

A Data Review Team (DRT) will monitor the study for safety on a regular basis (see [Section 10.3.1](#)).

The overall study design is described by a [study schema](#) at the end of the protocol synopsis section.

The study endpoints are defined in [Section 10.1.1](#).

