AE = adverse event; IV = intravenous; CT = computed tomography; CRP = C-reactive protein; ECG = electrocardiogram; ECOG PS = Eastern Cooperative Oncology Group performance status; HBsAg = hepatitis B surface antigen; HCVAb = hepatitis C virus antibody; HIV = human immunodeficiency virus; Ig = immunoglobulin; IP = investigational product; LDH = lactate dehydrogenase; MRD = minimal residual disease; PET = positron emission tomography; Q3 = every 3 months; EOS = end of study

^a Run-in period is up to 24 months in duration. During the run-in 1 period enrolled subjects that are MRD-negative/PET-CT negative will be followed at 3, 5, 7, 9 months and thereafter every 3 months (± 1 week) up to 24 months for MRD testing. At enrollment or during the run-in 1 subjects that are MRD-positive will complete Run-in 2 assessments to determine part 2 eligibility and treatment assignment.

^b **On days of hospitalization, obtain vital sign monitoring every 4 to 8 hours based on institutional standard of practice. When subject is in the outpatient clinic, only obtain 1 baseline vital sign per visit.**

^c Creatinine clearance is calculated by the Cockcroft-Gault equation

^d Pregnancy test must be performed within 72 hours from the start of run-in period and 72 hours prior to the first dose of blinatumomab (day [D] 1, cycle 1).

^e Lumbar puncture only required during treatment period if subject has a neurologic event leading to interruption/discontinuation or at seizure.

^f During the long term follow-up period an optional sample for MRD testing will be obtained at the time of suspicion of relapse and relapse.

^g PET-CT must be performed at run-in 2 in subjects that are MRD positive during run-in 1. Subjects that are MRD-positive at screening may qualify for treatment assignment with historical PET-CT negative results as long as PET-CT was performed ≤ 6 weeks from day 1 cycle 1 (first dose of blinatumomab) and subject has no clinical signs or symptoms suggestive of disease progression (eg, increase in LDH not otherwise explained). Every attempt should be made to complete PET and CT within 3 days of each other, particularly during blinatumomab treatment. PET-CT at day 71 (+ 3 days) will only be performed if subject remains MRD+ at cycle 1 day 57 or has clinical signs and symptoms of disease progression. During the long-term follow-up period a PET-CT or CT will be obtained at time of relapse and as per institutional standards for surveillance.

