MRD status will be assessed at cycle 1 day 1 prior to blinatumomab infusion, on cycle 1 days 15 and 43, the end of the blinatumomab infusion (day 57) and 2 weeks after the end of the blinatumomab infusion (day 71 + 3 days) to evaluate disease status. A PET-CT will be performed only if a subject remains MRD-positive (day 57 of cycle 1 assessment) after blinatumomab or has clinical signs and symptoms of disease progression.

A safety follow-up visit will occur 30 days (+ 3 days) after the last dose of blinatumomab for assessment of disease-related events, adverse events, and serious adverse events. A long-term follow-up period to assess disease status and OS begins at completion of the safety follow-up visit and continues for 1 year from the first dose of blinatumomab. Subjects will be followed via clinic visit every 3 months (\pm 2 weeks) for MRD assessment and by institutional standard of care disease evaluation (PET-CT or CT) until relapse at which time the subject will be followed for survival via telephone contact.

A Data Review Team (DRT) will monitor the study for safety on a regular basis.

The overall study design is described by a study schema below.

Study Design and Treatment Schema

EOS = end of study; IP = investigational product;; MRD = minimal residual disease; PET-CT = positron emission tomography/computed tomography

^a Run-in period is up to 24 months in duration. During the run-in period, enrolled subjects that are MRD negative/PET-CT negative will be followed at 3, 5, 7 and 9 months and thereafter every 3 months up to 24 months for monitoring of MRD status by next generation sequencing.

^b At any time after enrollment and during the run-in period subjects who turn MRD positive/ PET-CT negative and that meet all other part 2 eligibility will be assigned to treatment with blinatumomab. Subjects that do not display MRD positivity at the end of the 24-month run-in period will end the study.

^c MRD status will be assessed at cycle 1 day 1 prior to blinatumomab infusion, on cycle 1 days 15 and 43, the end of the blinatumomab infusion (day 57), and 2 weeks after the end of the blinatumomab infusion (day 71 + 3 days).

^d Long-term follow-up period will be 1 year from the first dose of blinatumomab. Subjects will be followed via clinic visit every 3 months (± 2 weeks) until relapse and from this point onwards via telephone contact for overall survival.

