To describe the relationship between clinical outcomes and baseline covariates and response to blinatumomab treatment	MRD negative rates in subgroups specified in section 4.2 will be presented using Primary and Full Analysis Sets	A sensitivity analysis will be performed using the Target Dose Analysis Set for the final analysis
To describe MRD status relative to clinical relapse	KM analysis of PFS and OS stratified by MRD response status after cycle 1 (landmark analysis on Day 75) will be performed in both Primary and Full Analysis Sets	A sensitivity analysis will be performed using the Target Dose Analysis Set for the final analysis
The percentage of MRD positivity in PET-CT negative subjects post aHsCT	Summary of subject who had PET-CT negative status post aHsCT and become MRD positivity status during run in period will be presented with pretreatment analysis set.	A sensitivity analysis will be performed using the Target Dose Analysis Set for the final analysis
Rate and timing of MRD negative to MRD positive change during the 24-month run-in period	Summary of MRD Status in different time points will be presented during run in period with pretreatment analysis set.	A sensitivity analysis will be performed using the Target Dose Analysis Set for the final analysis

Exploratory efficacy endpoints will be analyzed at primary analysis by using primary analysis set and pretreatment analysis set, and at final analysis using the Full analysis set.

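### The day-75 PFS landmark by MRD status drops symptom-free relapses found on a PET-CT that is routine only for subjects MRD-positive at day 57

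*SAP*

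**What the plan says.** The exploratory objective of describing MRD status relative to clinical relapse is met in SAP Table 9-3 by "KM analysis of PFS and OS stratified by MRD response status after cycle 1 (landmark analysis on Day 75"). SAP 9.5.3 gives the details:

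- Time point: "A landmark analysis will be performed using day 75 (end of cycle 1) as the landmark time point". (Cycle 1 is elsewhere 84 days long; that label needs reconciling separately.)
- Grouping: "Subjects will be defined as MRD negative or positive based on their MRD status as of at day 75".
- Risk set: "Only subjects who are still being followed up for PFS or OS at day 75 will be included in the analysis".

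The imaging rule is in Protocol Section 7.1, Table 4, footnote g: "PET-CT at day 71 (+ 3 days) will only be performed if subject remains MRD+ at cycle 1 day 57 or has clinical signs". The second trigger there covers any sign or symptom that points to progression. SAP 3.1 repeats both triggers: "A PET-CT will be performed only if a subject remains MRD-positive (day 57 of cycle 1 assessment) after blinatumomab or has clinical signs and symptoms". After cycle 1, disease is followed "by institutional standard of care disease evaluation (PET-CT or CT) until relapse" (Protocol 3.1), with no fixed scan schedule.

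SAP Section 5 dates a PFS relapse at diagnosis, whether by PET-CT, CT, clinical assessment or biopsy. The only sensitivity analysis listed for this landmark repeats it in the Target Dose Analysis Set. SAP 8.4 refers methods for detecting bias to the individual endpoint analyses, and 9.5.3 contains none.

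**The concern.** A landmark comparison of two groups needs events before the landmark to be found equally well in both. Here they are not. The last scheduled look before day 75 is a PET-CT whose routine trigger is the day-57 MRD result, which is closely related to the grouping variable.

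A subject MRD-positive at day 57 with a symptom-free relapse has it diagnosed on day 71 to 74 and is removed from the PFS risk set. A subject MRD-negative at day 57 with the same relapse is not scanned, enters as event-free and contributes an event after day 75. The MRD-positive curve is raised by removals that have no counterpart among the MRD-negative, and the MRD-negative curve carries relapses that were already present. Both effects tend to shrink the apparent benefit of MRD negativity.

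At stake is the study's own description of how MRD response relates to relapse. Protocol 2.4 rests the rationale on improving PFS by eradicating MRD.

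**Working it through.** **1. Timing.** The scan is on day 71 with a window of +3 days, so the latest in-window day is 71 + 3 = 74, before the landmark at day 75. Part 2 eligibility requires a negative PET-CT, so a scan positive for lymphoma is a new relapse. If it is dated at the scan, it is a PFS event before the landmark.

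**2. Next visit at which imaging might be expected.** Infusion ends at day 57, the safety visit is 30 days later and the first long-term visit about 90 days after that: 57 + 30 + 90 = 177.

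**3. Plan figure.** The plan gives no number for this analysis. SAP Table 3-1 is used only for group sizes. Its row 9/30 (14.7 to 49.4) reproduces as an exact binomial interval and implies 9 MRD-negative and 21 MRD-positive subjects.

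**4. Illustration with no true difference.** Assumptions: both groups have the same exponential hazard of PET-detectable relapse from day 1; every MRD-positive subject is scanned at day 71; MRD-negative relapses that are not clinically apparent are first found at day 177. Let s(t) = 2^(−t/m), where m is the median.

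- MRD-positive, reported PFS at day 177: s(177)/s(71).
- MRD-negative, none clinically apparent before day 75: s(177).
- MRD-negative, half of the relapses present at day 71 clinically apparent and so removed: s(177)/[s(71) + (1 − s(71))/2].

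| m | Removed by scan, 1 − s(71) | MRD-positive | MRD-negative, none apparent | MRD-negative, half apparent |
|---|---|---|---|---|
| 106.5 d (3.5 months) | 0.370 | 0.502 | 0.316 | 0.316/(0.630 + 0.185) = 0.388 |
| 213 d (7 months) | 0.206 | 0.708 | 0.562 | 0.562/(0.794 + 0.103) = 0.627 |

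The false gaps are 0.186, 0.114, 0.146 and 0.081, that is, about 8 to 19 points against MRD negativity. The 3.5 months is the lead time quoted in Protocol 2.2 for patients with detectable circulating tumor DNA. Here it only sets a scale.

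**5. Illustration with a true difference.** Let q be the share of MRD-negative subjects with imaging-detectable relapse by day 74, c the share of those found clinically before day 75, and P the later PFS, to the end of one-year follow-up, in subjects truly relapse-free at day 75. Reported MRD-negative PFS = (1 − q)P / [(1 − q) + q(1 − c)].

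Assume P = 0.70 for MRD-negative and 0.50 for MRD-positive, with early relapse in 30% of MRD-positive (0.30 × 21 = 6.3 subjects dropped) and q = 0.10:

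- c = 0: 0.63/1.00 = 0.630, difference 13 points.
- c = 0.3: 0.63/0.97 = 0.649, difference 15 points.
- c = 0.6: 0.63/0.94 = 0.670, difference 17 points.
- c = 1: 0.63/0.90 = 0.700, difference 20 points, the same as if both groups were scanned.

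Counted from day 1 with no exclusion, the difference is 0.90 × 0.70 − 0.70 × 0.50 = 0.28. The step from 28 to 20 is ordinary landmark conditioning; only the step from 20 to 13 comes from unequal imaging. With q = 0.20 and c = 0 the planned difference falls to 0.56 − 0.50 = 6 points. If q = 0 or c = 1, the formula returns P and there is no added bias.

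**6. Check of the day-57 landmark.** Under step 4 with none apparent, a day-57 landmark loses no one before the scan. At day 177 both groups read s(177) = 0.316, so the false gap closes. Between day 71 and day 177, however, MRD-positive reads 0.630 and MRD-negative 1.000, because MRD-positive relapses are found earlier.

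**The case against.** The strongest reply is that the imbalance may be small. Clinical signs trigger the scan whatever the MRD status. Read by column position (the table text is broken), Table 4 also places a clinical tumor assessment and LDH at day 71 for all treated subjects. The protocol names an unexplained LDH rise as suggestive of progression, and clinical assessment alone can establish a PFS event. So relapses also leave the MRD-negative group before day 75. This stands: the asymmetry concerns symptom-free relapses only. A reader might infer that only MRD-positive subjects are scanned, or that no early relapse leaves the MRD-negative group. The documents support neither.

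Second, the scan follows day-57 MRD while the groups use status as of day 75. A subject positive at day 57 and negative at day 71 is scanned, yet is MRD-negative at the landmark; the reverse case is MRD-positive and unscanned. This also stands. It blurs the bias without removing it, and the calculations above ignore it.

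Third, equal hazards is hard to believe. Protocol 2.2 cites a negative predictive value of 97.8% (92.2 to 99.7), though after frontline treatment. If q were 1 − 0.978 = 0.022 with c = 0, the MRD-negative curve would fall from 0.700 to 0.978 × 0.700 = 0.685. At the lower limit, q = 0.078, it would fall to 0.645. The loss is then about 1.5 to 5.5 points. This is fair, and it makes the 8 to 19 points an illustration and not an estimate.

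Finally, a scan outside its window, a later biopsy date or visits shifted by an interruption could put the diagnosis after day 75. Read literally, the risk-set sentence might also keep a relapsed subject who is still followed for OS. The second point is a reason to clarify the wording.

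**Conclusion.** The point holds in a limited form. Symptom-free relapses are removed before the PFS landmark unequally by MRD status, through the plan's own imaging rule, and no listed analysis reveals it. The direction is towards a smaller PFS advantage for MRD negativity.

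The size rests on a quantity that the documents do not give: silent relapse among MRD-negative subjects. The effect is nil if there is none or all is clinically evident before day 75. It is about 8 to 19 points at day 177 if hazards are equal and first detection is at that visit.

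A reader might infer that the analysis will hide or reverse the association between MRD and relapse. The documents do not support that, because it needs the equal-hazard assumption or something close to it. The analysis is also exploratory and descriptive, in about 30 subjects, with no formal test. The primary MRD-negative rate, whole-cohort PFS from first dose and the OS landmark are not affected.

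**What to change.** In SAP 9.5.3 and Table 9-3:

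1. Define the landmark risk set separately: subjects in PFS follow-up at day 75 for PFS, and subjects in OS follow-up at day 75 for OS.
2. Tabulate PFS events and exclusions before day 75 by day-57 MRD status, by day-75 MRD status, and by method of detection (MRD-triggered PET-CT, or clinical signs or assessment).
3. Add a sensitivity PFS landmark at day 57, grouped by day-57 MRD status, so that relapses on the triggered scan count at their date of diagnosis and are not dropped.

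Keep day 75 for OS. Do not reassign relapse dates or move subjects between MRD groups: the first would contradict the PFS definition, and the second would relabel subjects who became MRD-negative by day 71 and are responders under the primary endpoint.

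The cost is SAP wording, one table and one extra Kaplan-Meier run, with no new scans or data. The day-57 landmark has its own limits: it counts day-71 responders as MRD-positive and still finds MRD-positive relapses earlier. It should be read alongside the day-75 analysis, with emphasis on late time points such as 1 year.

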9.6 Safety Analyses

9.6.1 Analyses of Primary Safety Endpoint(s)

Table 9-4. Safety Endpoint Summary Table

Endpoint	Primary Summary and Analysis Method (Specify Analysis Set if FAS is Not Used)	Sensitivity Analysis
Adverse Event	The subject incidence of adverse events will be summarized for all treatment-emergent adverse events, serious adverse events, adverse events leading to withdrawal of protocol-specified therapy, and fatal adverse events. Primary Analysis Set at the time of Primary Analysis, and Final Analysis Set at the time of Final Analysis will be used for this analysis	Not applicable
Disease Related Events	Subject incidence of disease related events and fatal disease related events in the blinatumomab treatment period (through the safety follow-up visit) will be tabulated by system organ class and preferred term. Primary analysis set will be used for this analysis and Final Analysis Set at the time of Final Analysis will be used for this analysis	Not applicable
Laboratory Test Results	Shift tables between the worst post-baseline and baseline grades for selected laboratory parameters will be provided. The analyses of selected safety laboratory parameters including immunoglobulins, platelets, and liver parameters will include summary statistics over time. Primary Analysis Set at the time of Primary Analysis, and Final Analysis Set at the time of Final Analysis will be used for this analysis	Not applicable
Vital Signs	The number and percentage of subjects with abnormal changes in systolic blood pressure, diastolic blood pressure and heart rate will be summarized. Primary Analysis Set at the time of Primary Analysis, and Final Analysis Set at the time of Final Analysis will be used for this analysis	Not applicable
Electrocardiogram	summaries and statistical analyses of ECG measurements are not planned	Not applicable

Table 9-4. Safety Endpoint Summary Table

Endpoint	Primary Summary and Analysis Method (Specify Analysis Set if FAS is Not Used)	Sensitivity Analysis
Antibody Formation	The incidence and percentage of subjects who develop anti-blinatumomab antibodies (binding and if positive, neutralizing) at any time may be tabulated. Primary Analysis Set at the time of Primary Analysis, and Final Analysis Set at the time of Final Analysis will be used for this analysis	Not applicable
Exposure to Investigational Product	Descriptive statistics will be produced to describe the exposure to blinatumomab for subjects in the Primary Analysis Set at the time of Primary Analysis, and Final Analysis Set at the time of Final Analysis will be used for this analysis	Not applicable
Exposure to Concomitant Medication	Summarized by preferred term as coded by the World Health Organization Drug dictionary by Primary Analysis Set at the time of Primary Analysis, and Final Analysis Set at the time of Final Analysis will be used for this analysis	Not applicable

Page 2 of 2

9.6.2 Adverse Events

The Medical Dictionary for Regulatory Activities (MedDRA) version 21.1 or later will be used to code all events categorized as adverse events (AEs), disease-related events (DREs) to a system organ class and a preferred term. Treatment-emergent adverse events are events with an onset after the administration of the first dose of blinatumomab treatment through 30 days after the end of blinatumomab treatment. Adverse events of interest (EOI) categories will be based on search strategies defined by Medical Coding.

The subject incidence of adverse events will be summarized for all treatment-emergent adverse events, serious adverse events, adverse events leading to withdrawal of protocol-specified therapy, and fatal adverse events.

Subject incidence of all treatment-emergent adverse events, serious adverse events, adverse events leading to withdrawal of blinatumomab, leading to interruption of IP and fatal adverse events will be tabulated by system organ class and preferred term in descending order of frequency; similar summaries will be repeated for EOIs. Time to

onset and duration of selected EOIs (infection, neurologic events, and CRS) may also be summarized.

Any serious adverse event that occurs from enrolment through the day before the first dose of blinatumomab (during the run-in period) will be documented and summarized. This applies to all subjects who have been enrolled onto the study, regardless of whether they achieve the MRD-positive status required to start treatment with blinatumomab.

A summary of blinatumomab treatment-emergent adverse events will be tabulated by system organ class, preferred term, and worst grade.

